## **5.2 Demographics and Baseline Characteristics**

### **5.2.1 Demographics**

The date of obtaining informed consent, date of birth, sex, and study region will be recorded in the eCRF (date of birth and study region will be entered only for subjects who transferred from studies RAJ3 or RAJ4). Sex and weight will be confirmed at Week 0 and recorded in the CRF.

### **5.2.2 Medical History**

Diseases that remain uncured at the time of the first dose of study drug will be regarded as concurrent diseases. All concurrent diseases will be investigated, and the name of the diagnosis and the time of onset will be recorded in the medical record or other source document, as well as in the CRF (for subjects who were transferred from studies RAJ3 or RAJ4, the onset date of concurrent diseases does not need to be recorded in the CRF). Moreover, AEs that have continued to be present since studies RAJ1, RAJ3, or RAJ4 will be recorded in the CRF.

Previous diseases need not be recorded in the CRF.

### **5.2.3 Duration, Severity, Drug History, and Treatment Response of Target Disease**

The following items of information will be obtained at Week 0 and recorded in the CRF.

- RA dysfunction classification (1991 revised criteria) (Appendix 4)
- Duration of RA and classification of degree of progression (Appendix 5)

## **5.3 Efficacy and Pharmacodynamics Assessments**

### **5.3.1 Efficacy Assessments**

#### **5.3.1.1 Tender and Swollen Joint Counts**

- (1) Tender joint count

- CONFIDENTIAL -

At the time of each study visit (see Table 1, Schedule of Assessments), the investigator/sub-investigator will examine the subject for tender joints, assessing the 68 joints listed below, and confirm the location of each tender joint.

temporomandibular joint (2), sternoclavicular joints (2), acromioclavicular joint (2), shoulder joints (2)\*, elbow joints (2)\*, wrist joints (2)\*, DIP joints (8), PIP joints of both hands (10)\*, MCP joints (10)\*, hip joints (2), knee joints (2)\*, ankle joints (2), tarsal bones (2), MTP joints (10), interphalangeal joint joints of toes (2), PIP joints of both feet (8)

\*: Joints subject to DAS28 assessment

(2) Number of swollen joints

At the time of each study visit (see Table 1, Schedule of Assessments), the investigator/sub-investigator will examine the subject for swollen joints, assessing the 66 joints representing the aforementioned with the exception of the hip joints (2), and confirm the location of the swollen joints.

### 5.3.1.2 Assessment of Pain and Overall Assessment of Disease Activity

The following assessments will be performed at each study visit.

- (1) Subject's assessment of pain: The subject assesses his own pain severity on a VAS of 0-100 mm.
- (2) SGA: The subject assesses his own disease activity on a VAS of 0-100 mm.
- (3) PGA: The investigator/sub-investigator assesses the subject's disease activity on a VAS of 0-100 mm.

### 5.3.1.3 Acute Phase Reactants (CRP and ESR)

CRP and ESR will be measured at each study visit. The measurement of CRP will be performed by the central laboratory, and the measurement of ESR will be performed by each study center. These results will be used to calculate DAS28 (see Section 5.3.1.5, DAS28), SDAI (see Section 5.3.1.6, SDAI), and ACR response criteria assessment (see Section 5.3.1.7, ACR Response Criteria Assessment). ESR will be performed at the end of 1 hour, and the dates and results of measurements will be recorded in the eCRF.

### 5.3.1.4 EULAR Response Criteria

EULAR Response Criteria categorize response to treatment as "No response," "Moderate response," or "Good response," according to the definitions given in TTable 2 [van Gestel et al, 1996; van Gestel et al, 1998].

- CONFIDENTIAL -

**Table 2 Definition of EULAR Response Criteria Assessment**

DAS28 after treatment	DAS28 improvement (DAS28 before treatment - DAS28 after treatment)		
	> 1.2	> 0.6 and ≤ 1.2	≤ 0.6
≤ 3.2	Good response	Moderate response	No response
> 3.2 and ≤ 5.1	Moderate response	Moderate response	No response
> 5.1	Moderate response	No response	No response

**5.3.1.5 DAS28**

The subject's DAS28 will be calculated at each study visit (see Table 1, Schedule of Assessments), using data from the following assessments, together with the formula shown below [Prevoo et al, 1995; van der Heijde et al, 1990; Fransen et al, 2003; Mallya et al, 1982; Wolfe, 1997].

- TJC (28 joints)
- SJC (28 joints)
- CRP or ESR
- SGA

[When CRP is used]

$$\text{DAS28} = 0.56\sqrt{\text{TJC}} + 0.28\sqrt{\text{SJC}} + 0.36 \ln(\text{CRP} + 1) + 0.014 \times \text{SGA} + 0.96$$

[When ESR is used]

$$\text{DAS28} = 0.56\sqrt{\text{TJC}} + 0.28\sqrt{\text{SJC}} + 0.70 \ln \text{ESR} + 0.014 \times \text{SGA}$$

DAS28 score is assessed as below.

High disease activity: DAS28 score exceeding 5.1

Moderate disease activity: DAS28 score exceeding 3.2 to 5.1

Low disease activity: DAS28 score of less than or equal to 3.2

If the DAS28 score is less than 2.6, the subject will be considered to be in DAS28 remission [van Gestel et al, 1998; Fransen and van Riel, 2005].

**5.3.1.6 SDAI Score**

The SDAI score at each study visit will be calculated using data from the following assessments, together with the formula shown below [Smolen et al, 2003; Aletaha and Smolen, 2005; Felson et al, 2011].

- TJC (28 joints)
- SJC (28 joints)
- SGA
- PGA
- CRP (mg/dL)

$$\text{SDAI} = \text{TJC} + \text{SJC} + \text{SGA} + \text{PGA} + \text{CRP}$$

The SDAI score is assessed as below.

- High disease activity: SDAI score exceeding 26
- Moderate disease activity: SDAI score exceeding 11 and not greater than 26

- CONFIDENTIAL -

- Low disease activity: SDAI score exceeding 3.3 and not greater than 11

If the SDAI score is 3.3 or less, the subject will be considered to be in SDAI remission.

### 5.3.1.7 ACR Response Criteria Assessment

ACR Response Criteria [Felson et al, 1995] measure improvement in TJC, SJC, subject's assessment of pain, SGA, PGA, assessment of physical function using the Disability Index of the HAQ-DI, and acute phase reactant (CRP or ESR).

ACR20 response requires that all criteria (1) through (3) below be met. ACR50 response indicates a 50% improvement for all criteria (1) through (3) below, and ACR70 response similarly indicates a 70% improvement. For [5], assessment in this study is separately performed with regard to CRP and ESR.

- (1) TJC:  $\geq 20\%$  reduction compared to before administration of study drug
- (2) SJC:  $\geq 20\%$  reduction compared to before administration of the study drug
- (3)  $\geq 20\%$  improvement in 3 of the following 5 parameters, compared to before administration of study drug

- [1] Subject's assessment of pain
- [2] SGA
- [3] PGA
- [4] Disability Index (HAQ-DI)
- [5] CRP or ESR

### 5.3.1.8 Patient Reported Outcomes/Assessments

Subjects will complete the following questionnaires according to Table 1, Schedule of Assessments. The answers written in the questionnaire will be recorded in the eCRF.

- HAQ-DI [Fries et al, 1982; Ramey et al, 1992]
- SF-36v2® [Ware, 2004]
- WPAI [Takeuchi T, 2011; Reilly MC, 1993] (WPAI is only administered to subjects who transferred from studies RAJ3 or RAJ4)

### 5.3.2 Pharmacodynamics Assessments

Blood samples will be collected on the assessment days after the baseline as specified in the Schedule of Assessments. The measurements will be performed by the central laboratory. See Table 1, Schedule of Assessments, for the testing schedule. Results of the assessments and tests at Week 52 or follow-up of studies RAJ3 or RAJ4 that are to be used as the baseline data of this extension study will be reported to the sponsor and the study center after unblinding of the studies RAJ3 or RAJ4.

#### 5.3.2.1 Lymphocyte Subsets

Lymphocyte subsets CD3, CD4, CD8, CD16, CD19, CD56, and CD56/16 will be determined, and changes from baseline will be calculated. The day of blood sampling will be recorded in the eCRF.

- CONFIDENTIAL -

## 5.4 Safety Assessment

The following tests and observations will be made for the purpose of safety assessment. With the exception of urine tests for pregnancy testing, measurement of laboratory test values will be performed by the central laboratory. See Table 1, Schedule of Assessments, for the testing schedule.

Information on Liver Safety Monitoring and Assessment is given in Appendix 6. If an abnormality is found in the results of liver function tests, liver safety will be evaluated according to these procedures.

### 5.4.1 Vital Signs

Vital signs (body temperature, pulse rate, and blood pressure in sitting position) will be collected at each study visit, as shown in Table 1, Schedule of Assessments. The dates and results of measurements of vital signs will be recorded in the source document as well as in the eCRF.

### 5.4.2 Body Weight

Body weight will be measured according to Table 1, Schedule of Assessments. The dates and results of measurements will be recorded in the eCRF.

### 5.4.3 Adverse Events

The investigator/sub-investigator will confirm all AEs occurring in the period from the start of study drug administration to the end of the final observation. AEs will be handled according to the stipulations of Section 5.5, Adverse Events and Other Safety Aspects.

If an AE related to hepatic function abnormal is found, refer to the procedure in Appendix 6 entitled "Liver Safety Monitoring and Assessment."

If herpes zoster is reported, it will be recorded in the eCRF as adverse event information; a Herpes Zoster (shingles) Worksheet will be separately prepared, a copy of which will be submitted to the sponsor. For other AEs too, when the sponsor considers necessary and requests to submit additional information using a specific form, such a form must be filled out and submitted to the sponsor.

### 5.4.4 Laboratory Assessments

#### 1) Hematology, biochemistry (including fasting lipid profile tests), urinalysis

As shown in Table 1, Schedule of Assessments, the following hematology, biochemistry, fasting lipid profile tests, and urinalysis will be performed at each study visit.

Measurements will be made by the central laboratory. Dates of blood sampling for lipid profile tests will be recorded in the eCRF.

- Hematology  
Hemoglobin, hematocrit, erythrocytes (RBC), leukocytes (WBC), differential WBC (neutrophils, lymphocytes, monocytes, eosinophils, basophils), platelet count

- CONFIDENTIAL -

- Biochemistry  
Na, K, Ca, Cl, Mg, HCO3, BUN, phosphorus, glucose, creatinine, ALP, AST (GOT), ALT (GPT),  $\gamma$ -GTP, TBL, total protein, albumin, uric acid, CPK, LDH, serum amylase,  $\beta$ -D-glucan, eGFR
  - Fasting lipid profile tests  
Total cholesterol, LDL, HDL, TGs  
(Blood specimens for these tests should be drawn after the subject has fasted for at least 8 hours.)
  - Urinalysis  
pH, specific gravity, protein, glucose, keton bodies, bilirubin, occult blood, sediment
- 2) Pregnancy test (for females only)
- Urine pregnancy testing will be performed at the study visits every 12 weeks from Week 0 onward, as well as at end of treatment/early termination and end of study (at time of follow-up). The tests scheduled for the end of study (follow-up) will be performed only if the investigator/ sub-investigator decides necessary.
  - Urinalysis will be performed at each study center, using the kits provided by the central laboratory.
  - If a urine pregnancy test is positive at any time, a negative serum pregnancy test (with measurements performed by the central laboratory) is required for the subject to continue participation in the study. The study may be continued if the possibility of pregnancy can clearly be ruled out by other tests.
  - The pregnancy tests need not be performed if the possibility of pregnancy can clearly be ruled out, such as if the woman is postmenopausal or has not had a menstrual period for 1 year or more, or has had a hysterectomy, bilateral oophorectomy, etc.
  - Tests for pregnancy are not included in safety assessment.
- 3) Hepatitis tests
- A subject who has tested positive for either or both HBc and HBs antibodies at screening for studies RAJ3 or RAJ4 will be monitored by performing HBV-DNA assay at specified visits during the treatment period.  
Results of HBV-DNA assay after the baseline will not be included in safety analysis.
- 4) CPK monitoring
- At time of CPK elevation, CPK, CK-MB, troponin T levels, and aldolase levels will be measured according to Section 5.4.4.1, CPK Monitoring. As part of the physical examination, urinalysis (blood and microscopy) will be performed.

- CONFIDENTIAL -

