4. Subject who has tested positive for any of the following at screening for studies RAJ3 or RAJ4: HBs antigen, HBc antibody, HBs antibody, and HBV-DNA assay (However, if a subject is negative for HBs antigen and HBV-DNA assay, and positive for either or both HBc and HBs antibodies, the subject may be included provided that the subject is monitored by performing HBV-DNA assay at every scheduled visit after initiation of study drug administration.)
5. Subject has received a prohibited concomitant medication or prohibited concomitant therapy during the time from the end of the assessments at Week 52 of studies RAJ3 or RAJ4 to the first dose of the study drug in this extension study.
6. Subject has QTc < 300 msec on ECG measurements performed at the study site at Week 52 of studies RAJ3 or RAJ4 and has QTc < 300 msec at retest.
7. The subject has been judged unsuitable to participate in the study for other reasons by the investigator/sub-investigator.

[Rationale for exclusion criteria]

1-3: Established on the basis of general considerations for clinical studies.

4, 6: Established out of consideration for the safety of the subjects.

- CONFIDENTIAL -

- 5: Established to eliminate factors affecting the evaluation and out of consideration for the safety of the subjects.
- 7: In addition to 1 through 6 above, the exclusion criteria were established in light of scientific and ethical aspects of the study, envisioning situations in which the investigator/sub-investigator would deem a potential subject to be unsuited to participating in this study.

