### 3.4 Discontinuation Criteria for Individual Subjects

A discontinuation means that a subject who has enrolled in the study prematurely terminates study treatment prior to the completion of all protocol-required elements.

The subject is free to withdraw from the study treatment and/or study for any reason and at any time without giving reason for doing so and without penalty or prejudice. The investigator is also free to terminate a subject's involvement in the study at any time if this is considered necessary because of the subject's clinical condition.

Discontinuation Criteria for Individual Subjects:

The investigator/sub-investigator should discontinue the study if any of the following criteria are met:

1. Subject withdraws consent.
2. The study drug is not sufficiently effective, and a change in treatment method is deemed to be in the subject's best interest by the investigator or sub-investigator.
3. Symptomatic CPK elevation, defined as  $CPK > 1.5 \times ULN$  with severe unusual myalgia, muscular weakness, or muscle twitching\*.  
\* Muscle twitching: A condition in which there is a cramp in a muscle, such as cramps in the calves
4. Any event of myopathy defined as severe unusual myalgia, muscular weakness, and muscle twitching\* regardless of CPK level that persists for at least 2 weeks or that worsens rapidly within 2 weeks.  
\* Muscle twitching: A condition in which there is a cramp in a muscle, such as cramps in the calves
5. Subject infected with HBV who has tested positive for either of or both of HBc and HBs antibodies and is found to be positive for HBV-DNA assay during the study period. Abrupt discontinuance of immunosuppressive therapy may precipitate severe or fulminant hepatitis. Therefore, when HBV reactivates, nucleic acid analog therapy should be immediately initiated, and a hepatologist should be consulted regarding the continuation of ASP015K and concomitant DMARD (unique to Japan: as indicated by "Proposal for Management of Rheumatic Disease Patients with Hepatitis B Virus Infection Receiving Immunosuppressive Therapy" by the Japan College of Rheumatology).

- CONFIDENTIAL -

6. Subject has a malignant tumor.
7. Subject has an adverse event (AE) such as a serious infection, and the investigator or sub-investigator considers that it is not in the subject's best interest to continue the study.

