## 5.5 Adverse Events and Other Safety Aspects

### 5.5.1 Definition of Adverse Events (AEs)

An AE is defined as any untoward medical occurrence in a subject administered a study drug that does not necessarily have a causal relationship to this treatment. An AE can therefore be any unfavorable and unintended sign (including an abnormal laboratory finding), symptom, or disease temporally associated with the use of a study drug, whether or not related to the study drug.

All AEs newly observed in the period from the first dose of study drug to end of study (at time of follow-up) or spontaneously reported AEs will be recorded in the medical record or other source document, as well as in the CRF. If a concurrent disease has clearly worsened to an extent that exceeds the usual course after the first dose of the study drug, it will be mentioned among the AEs as a worsening of a concurrent disease. If an AE recurs after having temporarily disappeared, it will be handled as a new AE.

An abnormality identified during a medical test (e.g., laboratory parameter, vital sign, ECG data, physical examination) should be defined as an AE only if the abnormality meets one of the following criteria:

- Induces clinical signs or symptoms
- Requires active intervention
- Requires suspension, interruption, or discontinuation of study medication
- The abnormality or laboratory test value is clinically significant based on the opinion of the investigator or other responsible personnel

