7.5.2 Clinical Laboratory Evaluation

7.5.2.1 All Laboratory Tests

For clinical laboratory parameters (hematology, biochemistry, fasting lipid profile, and urinalysis), raw values at each scheduled visit, change from Week 0 at each post-Week 0 visit, shift from Week 0 and shift from reference range will be summarized using descriptive statistics or frequency tabulations. For Fasting Lipids Profile, all analysis will be conducted using the measured values which are confirmed under fasting condition. In addition, all Lipid

Profile values including non-fasting condition will also be summarized for descriptive statistics.

For subjects who shift from RAJ3, clinical laboratory test is conducted at central institution at each region (Japan, Korea, and Taiwan) in accordance with each procedure and each reagent for clinical test. The possibility of harmonization among each region was conducted before clinical laboratory test was initiated in Korea and Taiwan. If clinical laboratory evaluation could be harmonized, then these measurement data among each region could be regarded as the same scale. If harmonization was reported to be difficult, then clinical test would be summarized by Study Region (Japan, Korea, and Taiwan). However, among clinical laboratory tests not-harmonized, for exploratory analysis, Beta-D-glucan, Glucose, HCO3, urine pH, urine gravity will be summarized by whole population. Qualitative Urinalysis test will be summarized by Study Region, only (see 7.8.2 Subgroup analysis for Study Region (Japan, Korea, and Taiwan).

- Clinical laboratory tests harmonized
 - All of the hematology test
 - Biochemistry test except for Beta-D-glucan, Glucose, HCO3
 - All of the fasting lipid profile
 - CRP
- Clinical laboratory tests not-harmonized
 - Beta-D-glucan, Glucose, HCO3
 - All of the urinalysis test
 - * Pregnancy test, CPK monitoring, and Hepatitis test are not applicable to harmonization and it will be displayed in listing only.
- For continuous variables, descriptive statistics of raw values at each scheduled visit will be summarized at each time point using SI unit. For the ratio T-Chol to HDL and the ratio LDL to HDL, descriptive statistics will be summarized at each post-baseline visit.
- For continuous variables, descriptive statistics of change from Week 0 value will be summarized at each visit using SI unit.

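### No HBV-DNA conversion rate is planned for the antibody-positive RAJ3/RAJ4 subjects who are tested for it, because the protocol keeps post-baseline results out of the safety analysis and the SAP only lists them

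*Protocol*

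**What the plan says.** **Entry and monitoring.** Protocol 3.3 (exclusion criterion 4 for RAJ3/RAJ4) admits subjects positive for HBc and/or HBs antibody, but negative for HBs antigen and HBV-DNA, provided they are "monitored by performing HBV-DNA assay at every scheduled visit after initiation of study drug administration". Protocol Appendix 2 schedules the assay for RAJ3/RAJ4 subjects only, at Week 0 and then every 12 weeks.

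**Consequence of a positive result.** Discontinuation criterion 5 in Protocol 3.4 applies when an antibody-positive subject "is found to be positive for HBV-DNA assay during the study period". The same item says that "when HBV reactivates, nucleic acid analog therapy should be immediately initiated" and that "a hepatologist should be consulted regarding the continuation of ASP015K and concomitant DMARD".

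**Analysis.** Protocol 5.4.4, under hepatitis tests: "Results of HBV-DNA assay after the baseline will not be included in safety analysis". SAP 7.5.2.1: "Pregnancy test, CPK monitoring, and Hepatitis test are not applicable to harmonization and it will be displayed in listing only".

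**AE rule.** Under Protocol 5.5.1 a test abnormality becomes an AE only if it meets one of four conditions. Two of them are "Requires active intervention" and "Requires suspension, interruption, or discontinuation of study medication".

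**The concern.** Protocol 1.4 names reactivation of latent, chronic infection as a risk of this immunosuppressive drug. The study then tests a defined at-risk group for one such reactivation throughout treatment, and the analysis rule sets the results aside. What a reader of the study report would want is the number who converted among those monitored, and over how much follow-up. Neither document plans that figure.

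The stake is the safety conclusion. A few conversions, or none, will look more reassuring against the whole treated population than against the smaller group in whom conversion was looked for.

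**Working it through.** Neither document states a figure on this point, so there is none to reproduce. The check has two parts.

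**1. Which planned outputs could carry the information?**

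- *Laboratory tables (SAP 7.5.2.1 to 7.5.2.4).* The hepatitis test is listed only. Liver enzymes and bilirubin are summarised, but they show hepatic consequences, not viral conversion.
- *AE tables (SAP 7.5.1.1, 7.5.1.2).* A reactivation treated with an antiviral, or one that stops study drug, meets Protocol 5.5.1. It is then counted by SOC and PT and per 100 patient-years, by preceding study and overall. The denominator is the safety analysis set, not the monitored subjects.
- *AEs of special interest (SAP 7.5.1.1, Appendix 8).* HBV reactivation is not named. It would enter only if coded as an infection and either serious or treated with intravenous anti-infectives.
- *Baseline tables and subgroups (SAP 7.2.2, 7.8.1).* Hepatitis B antibody status appears in neither, so the at-risk denominator is not shown anywhere.
- *Withdrawals by primary reason (SAP 7.2.1).* Not a clean substitute, because criterion 5 also refers continuation of study drug to a hepatologist. A positive subject may or may not appear as a withdrawal.

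**2. How much does the denominator matter?**

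Inputs: about 800 treated subjects, of whom 201 come from RAJ1 (Protocol 7.1). Antibody prevalence is not given; 10% to 25% is an assumption for illustration. The 3 conversions are hypothetical.

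- RAJ3/RAJ4 subjects: 800 − 201 = 599.
- Monitored: 599 × 0.10 ≈ 60; 599 × 0.25 ≈ 150.

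Exact (Clopper-Pearson) 95% limits:

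| Denominator | 3 conversions | 95% limits | Upper limit if 0 conversions |
|---|---|---|---|
| 800 (overall column) | 0.38% | 0.08–1.09% | 0.46% |
| 599 (RAJ3 + RAJ4) | 0.50% | 0.10–1.46% | 0.61% |
| 150 monitored | 2.0% | 0.41–5.73% | 2.43% |
| 60 monitored | 5.0% | 1.04–13.92% | 5.96% |

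Dilution in the overall column: 800/150 = 5.3-fold to 800/60 = 13.3-fold. Within the RAJ3 or RAJ4 column RAJ1 subjects do not contribute, so dilution is about 1/0.25 = 4-fold to 1/0.10 = 10-fold, if prevalence is similar in the two studies.

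**The case against.** The strongest reply is that the Protocol 5.4.4 sentence concerns the assay as a laboratory variable and does not remove reactivation as an event. Since the protocol calls for antiviral therapy on reactivation, a case managed as directed is an AE by rule and reaches the incidence and per-100-patient-year tables. That stands. A reader might infer from the exclusion sentence that the study cannot report reactivation at all. The documents do not support this: reported events are tabulated, results are listed, and conversions could be counted from the listing afterwards.

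Two further limits also stand. The denominator of 800 applies only to the overall column. And a reader might suppose that a detected/not-detected count needs no cross-region harmonization, but neither document shows that the assay or its detection limit is the same in Japan, Korea and Taiwan. SAP 7.5.2.1 says that RAJ3 laboratory tests used each region's own procedures and reagents.

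The reply does not close the gap. The AE route uses a broader denominator, and the protocol does not say that every positive assay is a reactivation, so a positive that meets none of the four AE conditions appears in no summary. Nor does lack of harmonization explain listing only: the same SAP section summarises several tests that could not be harmonized, by region or exploratorily in the whole population. RAJ4 enrolled only Japanese subjects (Protocol 1.3), so the cross-region problem does not arise there.

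**Conclusion.** The point holds in a limited form. Post-baseline HBV-DNA is excluded from the safety analysis by an explicit rule, and no conversion rate is pre-specified among the antibody-positive RAJ3/RAJ4 subjects monitored for it. The AE tables partly compensate, but they understate the proportion among those at risk and leave out positives not recorded as AEs.

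Under the assumed 10% to 25% prevalence, the understatement is about 5- to 13-fold in the overall column and 4- to 10-fold in the columns by preceding study. The sizes depend wholly on that assumption; the gap itself does not. The two documents agree with each other on the exclusion, and no hypothesis test is affected. This is an inexpensive improvement to safety reporting, not an error that undermines the study.

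**What to change.** 1. **Protocol 5.4.4.** Replace the exclusion sentence with a statement that post-baseline HBV-DNA results in antibody-positive subjects will be summarised as the SAP specifies.

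2. **SAP 7.5.2.** Add one table for RAJ3/RAJ4 subjects who were HBc and/or HBs antibody-positive at screening: number monitored (at least one assay after Week 0), number and percentage with any positive HBV-DNA after Week 0, patient-years, and incidence per 100 patient-years with an exact Poisson 95% interval. Present it by preceding study, and by region within RAJ3 because assay comparability is not documented. Define time at risk as first dose to first positive or last assay. The interval formula in SAP 7.5.1.2 takes the logarithm of the event rate and so cannot be computed with zero events, a likely result here; hence the exact method. Keep the listing.

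3. **Scope note.** State that RAJ1 subjects are not covered, since the assay is not scheduled for them.

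4. **Passages to reconcile.** Protocol 3.3 requires testing at all scheduled visits, whereas 5.4.4 refers to specified visits. Appendix 2 lists the 12-weekly RAJ3/RAJ4 visits, so the two may coincide, but the wording should match. Criterion 5 in Protocol 3.4 lists positivity as a reason to discontinue and also refers continuation to a hepatologist. The sponsor should reconcile these so that positives, reactivations and withdrawals can be classified consistently.

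Cost: one short table from data already collected and already going to a listing. Its intervals will be wide.
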